4.1. General Considerations

Statistical analysis of this study will be the responsibility of the Sponsor or its designee.

Unless otherwise noted, tests of treatment effects will be conducted at a 2-sided alpha level of 0.05 (or equivalently, a 1-sided 0.025 alpha level); 2-sided CIs will be displayed with a 95% confidence level. If relevant, tests of interactions between treatment and other factors will be conducted at an alpha level of 0.05.

Participant assignment to treatment will be stratified by ApoE ϵ 4 genotype, and baseline amyloid level. These factors will be included in analysis models unless otherwise stated.

All amyloid plaque analyses will follow the ITT principle unless otherwise specified. An ITT analysis is an analysis of data by the groups to which participants are assigned by random allocation, even if the participant does not take the assigned treatment, does not receive the correct treatment, or otherwise does not follow the protocol.

When change from baseline is assessed, participants will be included in the analysis only if both a baseline and a postbaseline measure are available. Unless otherwise defined, a baseline measure is the last non-missing observation collected prior to the first administration of study medications. Endpoint is the last non-missing post-baseline measurement.

To allow for sequential testing, database locks and the testing of corresponding primary and key secondary objectives are expected to occur after all randomized participants have had a chance to complete the scheduled 24-week PET scan, the scheduled 52-week PET scan, and the scheduled 76-week PET scan. If an interim analysis occurs, a database lock will additionally occur after a sufficient number of participants (for example, approximately 75-125) have had a chance to complete the scheduled 24-week PET scan. Data collected during the immunogenicity and safety follow-up period will be summarized and analyzed separately.

Any change to the data analysis methods described in the protocol will require a protocol amendment only if it changes a principal feature of the protocol. Any other change to the data analysis methods described in the protocol, and the justification for making the change, will be described in the SAP and the clinical study report. Additional exploratory analyses of the data will be conducted as deemed appropriate.

4.2. Participant Dispositions

Reason(s) for study discontinuation will be summarized by treatment group for all randomized participants. The percentage of participants discontinuing from each treatment group will be compared between groups using Fisher's exact test. The comparisons will be done for the overall percentage of participants who discontinue and for select specific reasons for discontinuation. The reason(s) will be collected and will be summarized by treatment group for all randomized participants. The percentage of participants discontinuing from each treatment group will be compared between groups using Fisher's exact test. The comparisons will be done for the overall percentage of participants who discontinue and for select specific reasons for discontinuation.

4.3. Patient Characteristics

Baseline characteristics will be summarized for the randomized population by treatment group and overall. Summaries will include descriptive statistics for continuous and categorical measures. Patient characteristics to be presented include:

- age
- gender
- race
- ethnicity
- height
- body weight
- body mass index (weight (kg) / [height (m)]²)
- tau PET burden (various measures)
- APOE4 carrier status (carrier [$\epsilon 2/\epsilon 4$, $\epsilon 3/\epsilon 4$, $\epsilon 4/\epsilon 4$], noncarrier [$\epsilon 3/\epsilon 3$, $\epsilon 2/\epsilon 2$, $\epsilon 3/\epsilon 2$])
- APOE4 genotype ($\epsilon 2/\epsilon 4$, $\epsilon 3/\epsilon 4$, $\epsilon 4/\epsilon 4$, no $\epsilon 4$)
- AChEI and/or memantine use at baseline
- Baseline CDR
- Baseline MMSE
- Baseline Amyloid PET centiloids

4.4. Co-Primary Endpoints Analysis

The primary objectives of this study are to test the hypothesis that participants treated with donanemab will have a significantly greater proportion of participants who reach amyloid plaque clearance compared to participants treated with aducanumab at the 6-month timepoint in both the ITT population and the intermediate tau subpopulation.

As the 6-month timepoint is the first scheduled opportunity to collect a post-baseline florbetapir F18 PET scan, the comparison of donanemab to aducanumab in complete brain amyloid clearance at 6 months will be performed using logistic regression. The logistic regression model will include fixed effect for treatment, ApoE $\epsilon 4$ genotype, baseline amyloid level, and baseline age. The test for this endpoint will be based on the contrast for the main effect of treatment from this logistic regression model. This analysis will be conducted on the full ITT population and the intermediate tau subpopulation. In case of quasi-complete separation of data points which may be possible due to small sample sizes, a Firth's penalized logistic regression model will be used to make inference on treatment efficacy.

Treatment effects from these logistic regression models will be summarized using estimated probabilities within each treatment group, along with odds ratios and a 100*(1- α)% confidence intervals, where α is the two-sided significance level for the primary endpoints.

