9.5. Sample Size Determination

Approximately 200 participants will be enrolled and randomized in a 1:1 ratio to the 2 treatment regimens (donanemab and aducanumab). It is expected that approximately 180 participants will complete 6-month florbetapir F18 PET scans (approximately 90 per treatment regimen). It is

further anticipated that approximately 50% of participants randomized will belong to the intermediate tau subpopulation.

This sample size will provide at least 98% power to demonstrate that donanemab is superior to aducanumab in achieving complete amyloid brain plaque clearance individually at 6 months in the overall population and the intermediate tau subpopulation. Power estimates were obtained using specific contrasts for the 6-month time point of treatment by time interaction effect within the framework of generalized linear mixed effect model assuming a logit link.

The assumptions for this power calculation are that 35.7%, 50.1%, and 54.6% of donanemab treated participants reach complete brain amyloid clearance at 6 months, 12 months, and 18 months, respectively. The corresponding complete brain amyloid clearance percentages for aducanumab treated participants are assumed to be 3.0%, 22.8%, and 27.8%, respectively. The simulation for the power calculation and sample size determination was carried out in SAS Enterprise Guide Version 7.15 and all sample size estimates were obtained assuming a 2-sided significance level of 0.05.

10. Supporting Documentation and Operational Considerations

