4.9. Interim Analyses

A planned interim analysis may be conducted for Study AACN as deemed by Lilly or its designee to assess for early efficacy of the two co-primary endpoints. No changes to the conduct of the study will result from executing an interim analysis, nor will the results of the interim impact the conduct of the study. Should an interim analysis be deemed necessary, it will be

performed by the independent data monitoring committee (IDMC), consisting of a minimum of 3 external members, including a physician with expertise in AD and a statistician who are independent experts not otherwise involved in the study, when approximately at least a sufficient number of participants (75-125) overall have had a chance to receive their 6-month amyloid PET scan. The analysis method for the primary efficacy endpoint described in Section 4.4 Co-Primary Endpoint Analysis will be used for the interim analysis.

Alpha Spending Approach for the Potential Interim Analysis Based on the group sequential design with the Pocock alpha spending approach, a 2-sided alpha of 0.03100566 will be allocated to the interim analysis for evaluating the efficacy of each of the two co-primary endpoints. If either of the null hypothesis for the two co-primary endpoints are not rejected at the interim analysis, both co-coprimary endpoints will be evaluated at the originally scheduled time point when all randomized participants have had a chance to complete their 6-month amyloid PET scan. This analysis would be performed at a 2-sided alpha level of 0.02774 to maintain strong control of an overall 2-sided Type I error rate of 5%.

The 2-sided alpha levels specified above were calculated assuming an information fraction of 0.50 or when data is available on 50% of participants. Depending on the actual information fraction at the time of the interim analysis, the alpha levels for the interim and final time points will be adjusted accordingly, but the Pocock spending function will still be utilized. The information fraction will be defined as the number of patients who were randomized prior to a specified date (patients included in the interim) divided by the total number of patients randomized.

If the interim analysis is deemed not necessary to be conducted by the sponsor, the primary efficacy analysis will be conducted when all participants have had a chance to receive their 6-month amyloid PET scan. This will be conducted at the two-sided significance level of 5%.

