4.10. Changes to Protocol-Planned Analyses

There are no changes to the protocol planned analyses at this time.

5. Sample Size Determination

This sample size will provide at least 98% power to demonstrate that donanemab is superior to aducanumab in achieving complete amyloid brain plaque clearance individually at 6 months in the overall population and the intermediate tau subpopulation. Power estimates were obtained using specific contrasts for the 6-month time point of treatment by time interaction effect within the framework of generalized linear mixed effect model assuming a logit link.

The assumptions for this power calculation are that 35.7%, 50.1%, and 54.6% of donanemab treated participants reach complete brain amyloid clearance at 6 months, 12 months, and 18 months, respectively. The corresponding complete brain amyloid clearance percentages for aducanumab treated participants are assumed to be 3.0%, 22.8%, and 27.8%, respectively. The simulation for the power calculation and sample size determination was carried out in SAS Enterprise Guide Version 7.15 and all sample size estimates were obtained assuming a 2-sided significance level of 0.05.

6. Supporting Documentation

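### SAP 4.4 names no test statistic for the co-primaries and makes the Firth fit conditional on separation, which will be common in the intermediate tau set (minor)

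*SAP*

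**What the plan says.** SAP 4.4 compares the arms at 6 months by logistic regression on treatment, ApoE ε4 genotype, baseline amyloid and age, in the full set and in the intermediate tau set. The test is the treatment contrast. A fallback follows: "In case of quasi-complete separation of data points which may be possible due to small sample sizes", Firth's penalised model is used for inference. The section sets the confidence level through alpha. It does not say whether the contrast is Wald or likelihood ratio, which test and interval go with a Firth fit, or how separation is detected. Protocol 9.3.3 gives the logistic model with no Firth provision.

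For the optional interim, SAP 4.9 states: "The analysis method for the primary efficacy endpoint described in Section 4.4 Co-Primary Endpoint Analysis will be used for the interim analysis".

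The sample-size text in SAP Section 5 claims: "This sample size will provide at least 98% power to demonstrate that donanemab is superior to aducanumab", for each co-primary individually, and adds that "all sample size estimates were obtained assuming a 2-sided significance level of 0.05". The planning rates are "35.7%, 50.1%, and 54.6% of donanemab treated participants reach complete brain amyloid clearance at 6 months" (with the later months) and, for the comparator, "aducanumab treated participants are assumed to be 3.0%, 22.8%, and 27.8%, respectively". Protocol 9.5 gives the size: "Approximately 200 participants will be enrolled and randomized in a 1:1 ratio to the 2 treatment regimens", with about 180 completing the 6-month scan and about half in the intermediate tau subpopulation.

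**The concern.** The SAP treats separation as a possibility. At its own planning rates it is a routine event in the smaller co-primary set, because so few aducanumab clearances are expected. Two things follow.

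- The two co-primaries may be fitted by different methods at one look, and the tau co-primary by different methods at two looks.
- With sparse data and a large odds ratio, Wald and likelihood-based tests can disagree sharply. An analyst following SAP 4.4 could defend either, so a confirmatory decision could turn on a software default.

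SAP 2.1 requires both co-primaries to be met, so the tau test matters. An interim miss also has a price. Under SAP 4.9, the key secondaries have at least 0.03100566 available if both co-primaries are rejected at the interim, but 0.02774 if they are not.

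**Working it through.** **Inputs.** Clearance 35.7% versus 3.0% (SAP Section 5). 90 completers per arm, half in the tau set, so 45 per arm at the final analysis (Protocol 9.5). Interim at 75-125 participants, planned information fraction 0.50, alpha 0.03100566, then 0.02774 at the final (SAP 4.9). Tau set at the interim, per arm: 100 × 0.90 × 0.50 / 2 = 22.5, taken as 22 (17 from 75 participants, 28 from 125; 25 from 100 if no scans are missing).

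**The plan's own figures.** Two-proportion power is Φ{[|d|√n − z√(2p̄q̄)] / √(p₁q₁ + p₂q₂)}, with d = 0.327 and p̄ = 0.1935. At n = 45 and alpha 0.05: (2.194 − 1.960 × 0.5587) / 0.5086 = 2.16, so 98.5%. This reproduces the stated 98%. Pocock spending at 0.50 is 0.05 × ln(1 + 0.5(e − 1)) = 0.0310, and the matching final level is 0.02774. Both agree with SAP 4.9.

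**How often separation occurs.** The expected aducanumab clearances at 45 per arm are 45 × 0.03 = 1.35. The chance of none is:
- 0.97^45 = 25% (tau set, final)
- 0.97^22 = 51% (tau set, half-way interim; 60% at 17 per arm, 43% at 28)
- 0.97^90 = 6% (overall set, final)

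Separation can also arise through covariates. In simulation the total is roughly 27-29% at the tau final and 53-66% at a half-way interim, depending on the assumed covariate effects and scan completeness.

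**Why the test statistic matters: 22 per arm, alpha 0.031, no covariates.** In a 2×2 table the Firth fit equals adding 0.5 to each cell. The penalised likelihood-ratio (PLR) statistic is the likelihood-ratio statistic of that augmented table.

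- *8 versus 1, no separation, ordinary Wald:* log OR = ln(8/14) − ln(1/21) = 2.485; SE = √(1/8 + 1/14 + 1 + 1/21) = 1.115; z = 2.23, p = 0.026. Reject.
- *8 versus 0, separated, Firth Wald:* log OR = ln(8.5/14.5) − ln(0.5/22.5) = 3.273. With fitted p = 8.5/23 and 0.5/23, the information terms 22p(1 − p) are 5.126 and 0.468, so SE = √(1/5.126 + 1/0.468) = 1.527; z = 2.14, p = 0.032. Do not reject.
- *8 versus 0, Firth PLR:* 2[8.5 ln(8.5/4.5) + 0.5 ln(0.5/4.5) + 14.5 ln(14.5/18.5) + 22.5 ln(22.5/18.5)] = 10.36, p = 0.0013. Reject.

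The planned donanemab rate gives 22 × 0.357 = 7.9, so 8 is the expected count. Under Wald, stronger evidence fails where weaker evidence passes. Fitting Firth to 8 versus 1 as well does not cure this. The log OR is ln(8.5/14.5) − ln(1.5/21.5) = 2.129, the second information term becomes 22 × (1.5/23)(21.5/23) = 1.341, SE = 0.970, z = 2.19, p = 0.028, still below 0.032. PLR orders the tables correctly: for 8 versus 1 it is 2[8.5 ln(8.5/5) + 1.5 ln(1.5/5) + 14.5 ln(14.5/18) + 21.5 ln(21.5/18)] = 6.78, p = 0.009.

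**Power of the tau co-primary.** 3,000 simulated trials per setting with treatment, three-level ApoE, baseline amyloid and age. Assumed, not in the documents: ApoE split 30/53/17%, amyloid effect 0 or −1 log-odds per SD, and a Wald test of the ordinary fit. Monte Carlo standard error is 0.8-0.9 points at 22 per arm.

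| Per arm, alpha, amyloid effect | Switch, Wald throughout | Switch, PLR after Firth | Firth always, Wald | Firth always, PLR |
|---|---|---|---|---|
| 22, 0.031, none | 54.7% | 70.4% | 51.2% | 72.8% |
| 22, 0.031, −1 | 57.1% | 74.1% | 54.8% | 77.1% |
| 45, 0.02774, −1 | 98.8% | 99.1% | 98.5% | 99.3% |
| 45, 0.05, −1 | 99.3% | 99.4% | 99.2% | 99.4% |

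With no amyloid effect, final power is 97.7-98.0% for the switch against 98.5% for Firth-always PLR at 0.02774, and 99.1% against 99.2% at 0.05. An amyloid slope of 0.7 gives about 55% (Wald), 71% (switch, PLR) and 74% (Firth-always PLR) at the interim. From 17 to 28 per arm, holding alpha at 0.031 and with no amyloid effect, the ranges are 27.1-77.4% (switch, Wald), 52.5-83.7% (switch, PLR) and 54.4-86.3% (Firth-always PLR).

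**Splitting the gap (22 per arm, no amyloid effect).** Switch versus Firth-always, both with PLR: 72.8 − 70.4 = 2.4 points (3.0 with the amyloid effect). Wald versus PLR within the switch: 70.4 − 54.7 = 15.7 points.

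**Type I error.** Rejection in favour of donanemab under equal rates of 3% to 35.7%, switch with PLR: 0.1-2.1% at the interim (nominal 1.55%) and 0.9-2.2% at the final (nominal 2.5%). Firth-always PLR gives 0.1-2.1% and 0.9-2.5%. The 2.1% arises for both when both arms clear at 35.7%, so the switch does not cause it.

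**The case against.** The case for leaving the text alone is substantial. The fallback is declared in advance and anticipates this very problem. It adds no type I error. Final power is about 97-99% under every version. The interim is optional, does not alter conduct, and a missed co-primary is re-tested on the full data. Much of the low interim power is simply size and alpha: the unadjusted two-proportion formula at 22 per arm and 0.031 gives (1.534 − 2.157 × 0.5587) / 0.5086 = 0.65, or 74.1%. The SAP never says Wald, so the poor figures attach to one permitted reading. All of this stands, and it keeps the point minor.

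Three stronger readings might be inferred, and the documents support none of them.

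- *That the data-dependent switch itself loses much interim power.* It costs 2-3 points once Firth is tested by PLR. Firth-always with Wald is worse than the switch with Wald (51.2% against 54.7%).
- *That the tau co-primary, and so the trial, is at risk.* The final-analysis figures rule this out on the planning rates.
- *That the model uses four ApoE levels, one of them sparse enough to cause separation.* SAP 4.3 does list "APOE4 genotype" with four levels, but among baseline characteristics to be tabulated. SAP 4.1 puts the stratification factors into the models, and Protocol 6.3 gives that factor three levels.

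The objection does not reach the reversal between 8 versus 1 and 8 versus 0. That is a defect of the rule under a reading the SAP allows, whatever the average power.

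**Conclusion.** The point holds as a minor specification gap. SAP 4.4 leaves the test, the interval and the separation rule open for an analysis in which separation should be expected in about a quarter or more of tau finals and over half of half-way tau interims. Under a Wald reading the decision rule is not monotone in the evidence, and interim tau power is about 55% instead of 73-74% (57% against 77% with the stronger amyloid effect). Nearly all of that difference is Wald versus PLR. The separation frequencies rest on the plan's own 3.0% rate; a higher aducanumab rate would make separation rarer. The power figures also rest on the assumed ApoE split and amyloid effects. The worked 2×2 tables need only the interim size and alpha.

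**What to change.** State in SAP 4.4 that both co-primaries, at the interim and at the final 6-month analysis, are analysed by Firth penalised logistic regression whether or not separation occurs, with the penalised likelihood-ratio test for treatment and profile penalised-likelihood intervals for the odds ratio. No separation-detection rule is then needed. SAP 4.9 already points to 4.4, so it needs no change. Naming Firth without naming the test would not be enough, since the reversal persists under Firth with Wald.

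The cost is a sentence in the SAP and a standard software option. The downside is slightly shrunk odds ratios.

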4.4.1. Definition of endpoint(s)

Complete brain amyloid plaque clearance is a binary outcome and is defined as a centiloid value <24.1 from the florbetapir F18 PET scan.

4.4.2. Main analytical approach

As described above, the co-primary endpoints will be analyzed using logistic regression with the specified models for the full analysis set and for the intermediate tau analysis set. A missing 6-month PET scan will result in the participant being excluded from the analyses.

4.4.3. Sensitivity Analyses

A last-observation-carried-forward (LOCF) analysis for complete amyloid plaque clearance will be conducted. For participants without PET scan results at either 12 or 18 months, the centiloid measurement from their last available post-baseline PET scan will be used to determine complete amyloid plaque clearance for the missing assessments.

4.5. Key Secondary Endpoints Analysis

The mean change from baseline in amyloid plaque levels at months 6 and 12, the time to complete amyloid plaque clearance, and mean change from baseline in amyloid plaque levels at month 18 are the four key secondary endpoints. It is expected that these endpoints will be analyzed sequentially as data for them are available. That is, for any efficacy analyses for 6-month/12-month/18-months endpoints, data will be available at baseline and for all timepoints up to and including the time point in question.

4.5.1. Key Secondary Endpoints

4.5.1.1. Definition of endpoint(s)

For the 6-, 12-, and 18-month mean change analyses, change from baseline will be defined as the specific time point PET centiloid value minus the baseline PET centiloid value. For the time to complete amyloid plaque clearance analysis, participants will be categorized as either meeting criterion for complete amyloid plaque clearance based on florbetapir F18 PET centiloid values or not meeting this criterion. Time to event will be defined as the difference between the date of the PET scan which shows complete amyloid plaque clearance and the date of the first dose of study drug. Participants who do not meet this criterion will be censored at the time of their final PET scan.

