Vital signs	X	X	X	X	X	X	X	X	X	X	X	X	Vital signs include pulse rate, blood pressure, and temperature. Vitals should be measured after participant has been sitting for at least 5 minutes. Vital signs are measured prior to and within 30 minutes after infusion for clinical management, and not recorded in the CRF.
Weight (for aducanumab participants only)	X	X	X	X	X	X	X	X	X				Weight is measured prior to dosing with aducanumab only and is not recorded in the CRF.

	Open-Label Treatment											Short-term Follow-up	Comments
Visit Number	12	13	14	15	16	17	18	19	20	21	ET	801-804^	^Visit 801 to 804 may be used for return to baseline ADA monitoring and other safety assessments at discretion of the sponsor and may be requested within the time period listed.
Weeks relative to first infusion	40	44	48	52	56	60	64	68	72	76	-	84-120	
Visit interval tolerance (days)	±7	±7	±7	±7	±7	±7	±7	±7	±7	±7	-	±14	
MRI		X											MRI at V13 is to be performed and reviewed prior to V13 infusion. The MRI should occur at least 14 days after infusion at V12 is administered, and may occur outside of the visit windows. Unscheduled MRIs may be performed at the discretion of investigator, for example, if titration is delayed due to temporary suspension of infusions.
Florbetapir F18 PET scan				X						X	X		Collect at ET only if ET occurs at 3 or more IP infusions after the last florbetapir F18 PET scan.
Laboratory Tests and Sample Collections	In the event that study intervention is delayed, all laboratory collections should occur on the same day as study intervention infusion - and should be collected prior to infusion.												
Hematology and clinical chemistry				X						X	X		Collect prior to infusion.
PK sample				X						X	X	X	Collect prior to infusion. Predose collections may be collected from the IV site prior to the infusion.
Immunogenicity (ADA) samples				X						X	X	X	Collect prior to infusion.

	Open-Label Treatment											Short-term Follow-up	Comments
Visit Number	12	13	14	15	16	17	18	19	20	21	ET	801-804^	^Visit 801 to 804 may be used for return to baseline ADA monitoring and other safety assessments at discretion of the sponsor and may be requested within the time period listed.
Weeks relative to first infusion	40	44	48	52	56	60	64	68	72	76	-	84-120	
Visit interval tolerance (days)	±7	±7	±7	±7	±7	±7	±7	±7	±7	±7	-	±14	
Stored Samples													
Exploratory biomarker samples				X						X	X		Collect prior to infusion.

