9.3.4.2. Time to Amyloid Plaque Clearance

Time to amyloid plaque clearance between the two treatment groups will be analyzed and compared using a log-rank test for survival data. Time to amyloid plaque clearance is defined as the earliest time (6/12/18 months) at which the participant reaches plaque levels below a certain pre-defined threshold. Subjects who do not have their plaque cleared by the end of the study period or those who drop out prior to the end of the study without achieving amyloid plaque clearance will be censored at their last available time point. Kaplan-Meier estimates of percent of patients reaching amyloid plaque clearance and p-value from the log-rank test will be used to determine the superiority of donanemab vs aducanumab in lowering time to plaque clearance. Additionally, time to plaque clearance may also be analyzed using a Cox proportional-hazards model. More details on these analyses will be provided in the SAP as appropriate.

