4.5.1.2. Main analytical approach

As there is only one post-baseline PET assessment within the first 6 months of the trial, mean change from baseline in amyloid plaque levels at Month 6 will be analyzed using an analysis of covariance model with the treatment group as fixed effect variable of interest, and APOE e4 genotype, baseline amyloid levels, and baseline age as the covariates. For the analysis of mean change from baseline at 12 and 18 months, a separate mixed model repeated measures (MMRM) analysis with data up to and including that specific time point will be used. This model will include the fixed effects of treatment, time, and treatment by time interaction, and APOE e4 genotype, and baseline amyloid level as covariates. Correlation among repeated measures on the same subject will be accounted for by enforcing an unstructured variance covariance matrix among the residuals. If the unstructured covariance structure matrix results in a lack of convergence, the following structures will be used in sequence until convergence is reached: heterogeneous Toeplitz covariance structure, heterogeneous autoregressive covariance structure,

heterogeneous compound symmetry covariance structure, and compound symmetry covariance structure. The Kenward-Roger approximation will be used to estimate the denominator degrees of freedom.

Time to amyloid plaque clearance between the two treatment groups will be analyzed and compared using a log-rank test for survival data. Kaplan-Meier estimates of percent of participants reaching amyloid plaque clearance and the p-value from the log-rank test will be used to determine the superiority of donanemab vs aducanumab in lowering time to plaque clearance.

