4.5.1.4. Other secondary analyses

Mean percent change from baseline in brain amyloid plaque is defined as the specific time point PET centiloid value minus the baseline PET centiloid value, divided by the baseline PET centiloid value. These values will be modelled with the same approach as outlined for the mean change analyses.

Non-inferiority analyses will compare the changes in brain amyloid plaque levels for donanemab at 6 months to the changes in brain amyloid plaque levels for aducanumab at 12 months and at 18 months. The non-inferiority margin of interest is 5 centiloids. The MMRM models specified for the key secondary comparisons at 12 and 18 months will be used for the non-inferiority test, with appropriate contrasts and confidence intervals for the treatment-by-time interaction effects. For these non-inferiority analyses, if the upper bound of the 95% confidence interval for the donanemab vs. aducanumab contrasts is <5 centiloids, donanemab at 6 months will be considered to be non-inferior to aducanumab at that particular time point. An additional secondary objective to test the superiority of donanemab in amyloid plaque reduction at 6 months versus aducanumab at 12 months will also use this MMRM model and contrast.

For both the full study population and the intermediate tau subpopulation, the 12-month and 18-month comparison of proportion of participants with amyloid plaque clearance for donanemab versus aducanumab will include repeated post-baseline amyloid plaque clearance status (Yes/No) measurements and will be analyzed using separate generalized linear mixed model (PROC GLIMMIX) as pseudo-likelihood-based mixed effects repeated measures analysis assuming binomial distribution with a logit link. These models will be analyzed using data for outcomes up to and including the time point in question. The GLIMMIX model will include fixed effects for treatment, month, treatment-by-month interaction, APOE e4 genotype, baseline amyloid level, and baseline age as covariates. An unstructured variance-covariance matrix will be used to model the correlation among repeated measures on the same individual. If model convergence is not reached lesser restrictive variance-covariance structures will be employed until model convergence is attained.

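### The SAP times plaque clearance by actual scan date, not at the protocol's 6, 12 and 18 months, so the end of the Kaplan-Meier curve can overstate clearance by about 5 to 10 points

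*SAP*

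**What the plan says.** Protocol 9.3.4.2 gives the endpoint three possible values: "Time to amyloid plaque clearance is defined as the earliest time (6/12/18 months) at which the participant reaches plaque levels" below the threshold. Participants who never clear, or who drop out uncleared, "will be censored at their last available time point". The section leaves further detail to the SAP.

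SAP 4.5.1.1 works on a calendar-day scale: "Time to event will be defined as the difference between the date of the PET scan which shows complete amyloid plaque clearance" and the first dose. For everyone else: "Participants who do not meet this criterion will be censored at the time of their final PET scan". SAP 4.10 reports no change from the protocol's analyses, although Protocol 9.3.1 and SAP 4.1 both require any change of method, with its justification, to be described in the SAP.

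SAP 4.5.1.2 states how the result is judged: "Kaplan-Meier estimates of percent of participants reaching amyloid plaque clearance and the p-value from the log-rank test will be used" to decide superiority. SAP 2.1 places this endpoint third of four in the gated key secondary sequence.

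The Schedule of Activities (Protocol 1.3) puts post-baseline florbetapir scans at Weeks 24, 52 and 76, each ±7 days. There is also an early-termination scan under a condition: "Collect at ET only if ET occurs at 3 or more IP infusions after the last florbetapir F18 PET scan". Neither document says on which day the Kaplan-Meier percentage is to be read.

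**The concern.** Clearance status is known only at three scan waves. Within a wave, the order in which participants happen to be scanned says nothing about who cleared sooner, yet the SAP definition treats that order as information.

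At Weeks 24 and 52 this does little harm without dropout, because uncleared participants stay at risk until their next scan. At Week 76 there is no next scan. Each uncleared completer is censored on their own scan date, while clearers scanned a few days later still count as events against a smaller risk set. The curve then ends too high in both arms. This needs no imbalance, no dropout and no out-of-window scan.

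At stake is the reported clearance percentage for a gated key secondary endpoint. Read at the end, the curve would disagree with the 18-month proportion in SAP 4.5.1.4. That analysis "will include repeated post-baseline amyloid plaque clearance status (Yes/No) measurements", so it uses the same scans by visit and should agree if cleared participants stay cleared. The precision of the between-arm difference in end-of-curve percentages also worsens.

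**Working it through.** **Inputs.** Cumulative clearance at 6, 12 and 18 months: donanemab 35.7%, 50.1%, 54.6%; aducanumab 3.0%, 22.8%, 27.8% (Protocol 9.5, SAP 5). About 90 evaluable per arm (Protocol 9.5). Scan days 168, 364 and 532, window ±7 days. Assumed here: the rates are cumulative first clearance, there is no dropout, timing is the same in both arms, and events precede censorings on the same day.

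**The plan's own figure.** The documents state no Kaplan-Meier value. Their 98% power for 35.7% versus 3.0% reproduces: 98.5% at 45 per arm and above 99.9% at 90 per arm, two-sided 0.05.

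**Formula.** Write S52 for the proportion uncleared after Week 52 and h for the chance of clearing at Week 76 given that:

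- donanemab: S52 = 1 − 0.501 = 0.499; h = (0.546 − 0.501)/0.499 = 0.0902
- aducanumab: S52 = 1 − 0.228 = 0.772; h = (0.278 − 0.228)/0.772 = 0.0648

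Suppose m participants are scanned on each of K days in the Week 76 wave. With k scan days left (today included), km are at risk and mh events are expected, so the day's survival factor is 1 − mh/(km) = 1 − h/k. Hence

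expected end-of-curve clearance = 1 − S52 × ∏(k=1..K) (1 − h/k).

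Example, K = 15: the product is 0.7364 for donanemab, giving 1 − 0.499 × 0.7364 = 63.3%; it is 0.8039 for aducanumab, giving 1 − 0.772 × 0.8039 = 37.9%.

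| Scan days in the Week 76 wave | Donanemab | Aducanumab | Excess (points) |
|---|---|---|---|
| K = 1, scheduled visit | 54.6% | 27.8% | 0, 0 |
| K = 3 (±1 day) | 58.0% | 31.6% | +3.4, +3.8 |
| K = 5 (±2 days) | 59.6% | 33.6% | +5.0, +5.8 |
| K = 11 (weekdays within ±7) | 62.2% | 36.7% | +7.6, +8.9 |
| K = 15 (every day within ±7) | 63.3% | 37.9% | +8.7, +10.1 |

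**Simulation**, 90 per arm, 4000 trials per pattern:

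- ±2 days: 59.6% and 33.5%. Even ±7 days: 63.1% and 38.0% (medians 61.8% and 36.1%).
- Dates peaked at the centre (rounded normal, assumed SD 1 and 3 days): 61.3% and 36.4%; 64.3% and 40.0%. Peaking does not remove the effect, and SD 3 days exceeds the 5 to 10 point range.
- An assumed 10 to 20% dropout after the 6-month scan, even ±7 days: about 64% and 38%.
- SD of the between-arm difference: 7.1 points at scheduled times, 9.6 at ±2 days, 14.7 at ±7 days.
- Read at day 532 with even ±7-day dates: 53.3% and 26.4%, SD 7.2. The overstatement is gone, but 7 of the 15 scan days fall after the read-out.

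**Effect on the test.** Log-rank size with equal timing (6000 trials): 5.2% under a null at donanemab rates and 4.7% at aducanumab rates. Power at the plan's rates (2000 trials): 99.2% with actual dates, 99.4% with scheduled times. If the arms' mean scan dates differed by an assumed 3 days, size would be 10.2% and 8.8% (1 day: 5.3% and 5.9%), against 4.7 to 5.2% with scheduled times. Nothing in the documents indicates such a difference.

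**The case against.** The strongest reply is that the harm depends on reading the curve at its very end, which no passage requires. At day 535 with even ±7-day dates the values are 55.3% and 28.8%, only 0.7 and 1.0 points high. Stopping once fewer than 10 remain at risk gives 56.9% and 32.4%. On that view the gap is an unstated read-out day. This stands as a limit on the claim, but it does not clear the plan: with no rule fixed in advance, the reported figure depends on a choice that can be made after the data are seen, in an open-label trial.

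Second, the gate turns on the log-rank p-value, which is sound under equal timing. The between-arm difference barely moves on average, from 26.8 points at scheduled times to 26.0 at ±2 days and 25.3 at ±7 days (63.25 − 37.94), so donanemab is not favoured. This stands too. But SAP 4.5.1.2 names the Kaplan-Meier percentages alongside the p-value, so they need to be right.

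Third, the protocol's bracketed months could be read as naming scan occasions that the SAP was free to time by date. That is possible, but replacing three scheduled times with continuous dates changes the definition, and SAP 4.10 should then say so.

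Fourth, the visit-based 18-month proportion comes from a covariate-adjusted model and need not match exactly. True, but excesses of this size would be due to the timing rule, not to adjustment.

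**Conclusion.** The concern holds. The two definitions differ and the difference is not declared; that part rests on the text alone. Applied as written and read at the end of the curve, the SAP definition overstates 18-month clearance in both arms: by 5.0 and 5.8 points (donanemab, aducanumab) if dates spread evenly over ±2 days, and by 8.7 and 10.1 points over ±7 days. The SD of the between-arm difference about doubles in the latter case. These sizes rest on the plan's assumed rates and on an assumed spread of scan dates, since the documents give only the window. The damage is to this endpoint's curve, percentages and precision. It does not reach the log-rank test under equal timing, power at the planned rates, or study-wise error. The change should be made, but it does not threaten the trial's main conclusions.

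**What to change.** In SAP 4.5.1.1:

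- Set the event time to the scheduled visit (6, 12 or 18 months) at which a value below 24.1 centiloids is first seen.
- Set the censoring time to the scheduled visit of the last PET scan, with those participants counted as at risk at that visit.
- Add a rule that maps an early-termination scan to a visit.

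Keep the actual-date analysis as a sensitivity analysis with a stated read-out day. Record in SAP 4.10 any departure from Protocol 9.3.4.2 that remains. Three scheduled times produce heavy ties, so name the tie-handling method for the Cox model in SAP 4.5.1.3.

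With scheduled times and no dropout, the Kaplan-Meier curve ends at the observed cumulative proportion. The cost is SAP wording and minor programming, with no new data and no loss of power at the planned rates.
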